**Table 3-1 Result of power simulations for the primary variable**

Treatment effect (mL)	Discontinuation rate	Sample size	Power
112	15%	650	90.3
112	20%	650	85.9
100	15%	650	80.9

Based on 10,000 simulated trials per scenario and 250 multiple imputations for each trial. Simulations were conducted using SAS/STAT® 13.1 software, Version 9.4 of the SAS System for Linux.

### Power for the secondary objectives

If statistical significance is achieved in the primary test, the tests for the secondary variables will be performed. The local significance level for each secondary null hypothesis will be determined based on the closed testing procedure shown in [Figure 2](#).

As differences in FEV1 to placebo for QAW039 150 mg once daily and montelukast 10 mg once daily appeared to be of similar magnitudes in study QAW039A2206, the power calculations for the two secondary objectives (change from baseline in daytime asthma symptoms and change from baseline in total daily SABA use) are based on the assumptions from the results of two studies comparing montelukast 10 mg once daily with placebo ([Reiss et al 1998](#), [Malmstrom et al 1999](#)). These studies suggest an averaged difference of 0.26 for change from baseline in daytime asthma symptoms between montelukast and placebo after 12 weeks of treatment and a SD of 0.94. The two studies also suggest an averaged difference of -1.34 point difference in the change from baseline in the number of daily SABA puffs between montelukast and placebo with a standard deviation of 3.82. We assume a clinically important true improvement of at least 0.5 in AQLQ+12 after 12 weeks of treatment for patients that remain on treatment and a standard deviation (SD) of 1. As shown in [Table 3-2](#) all secondary endpoints have an adequate conditional power once the primary null hypothesis has been rejected, but will each have an even higher conditional power once the null hypotheses relating to the other secondary variables have been rejected.

**Table 3-2 Power simulations for secondary variables**

	Daytime asthma symptoms	Total daily rescue medication use	AQLQ+12
Difference of effect ( $\delta$ )	-0.26	-1.34 number of puffs	0.5
SD ( $\sigma$ )	0.94	3.82 number of puffs	1
Local two-sided significance level once primary null hypothesis is rejected	0.0245	0.0245	0.001
Power	74%	97%	98%
Local two-sided significance level once primary and the other two secondary hypotheses are rejected	0.05	0.05	0.05
Power	83%	98%	> 99%

Power statements are based on 10,000 simulated trials per scenario and 250 multiple imputations using a jump-to-reference approach for each simulated trial. Simulations were conducted using SAS/STAT® 13.1 software, Version 9.4 of the SAS System for Linux. We assumed a treatment discontinuation rate of 15% with half of the patients discontinuing from study treatment completing the trial. The correlation structure was assumed the same as for the primary endpoint. Abbreviation: AQLQ+12 (asthma quality of life questionnaire for 12 years and older).

#### 4 Change to protocol specified analyses

- Section 9.2 in the study protocol states that the age of the patient will be calculated from the date of birth to date of Visit 1. However, since date of birth is not captured on the CRF page and age (in years) at the time of informed consent is entered into CRF, there is no need to re-calculate age.
- Shift tables relative to the normal reference ranges to summarize the on-treatment change from baseline to post-baseline for each laboratory parameter or ECG parameter or vital sign assessments will not be presented.
- Study protocol defines treatment emergent adverse events as those events starting on or after the time of the first intake of study drug and until the day after the last intake of study drug. However, in order to maintain consistency with the submission documents, for analysis purposes the following updated definitions are considered:  
AEs starting on or after the time of the first intake of study drug and not later than 7 days (30 days in the case of a serious AE) after the last intake of study drug will be classified as a TEAE.
- Added the responder analysis for AQLQ improvement
- Added more details to liver function tests including eDISH plot
- Added analysis for renal events and liver events according to project level alignment
- The following analyses, though pre-specified in the protocol, may not be critical for decision making purposes and hence will be reported outside of CSR:

█ [REDACTED]

- In protocol 9.4.4, supportive analysis for the primary endpoint based on other missing data imputation approaches: pattern mixture approach combining the jump to reference and missing at random approaches by distinguishing reasons for discontinuation of treatment and retrieved dropout imputation approach.
- In protocol Section 9.4.4, subgroup analyses for BMI, number of exacerbations in the previous year, ACQ tertiles, [REDACTED].
- Summaries on post-treatment discontinuation events to be produced for adverse events and serious adverse events by system organ class and preferred term.

## 5 Analyses to be reported outside of CSR

The following analyses are not planned for CSR reporting and will be conducted for data exploration after DBL. If any of the analyses are judged valuable for inclusion in the CSR, it will be added as additional exploratory outputs in the CSR.

### 5.1 Primary efficacy variable

#### 5.1.1 Subgroup analyses

Subgroup analysis on the primary variable for certain subgroups will be performed outside of CSR. Some of the subgroups are the following:

- Smoking status (Never, Former)
- Body Mass Index (BMI) ( $\leq 30.0 \text{ kg/m}^2$  and  $> 30.0 \text{ kg/m}^2$ )
- Atopic asthma at entry into study (yes, no)
- Baseline ACQ-5 (tertiles 1, tertiles 2, tertiles 3)
- Severity of asthma (GINA step 3, step 4) at baseline

#### 5.1.2 Supportive analyses

##### Alternative pattern mixture imputation

Data will be analyzed in the same manner as for the primary analysis. Intermittent missing data for QAW039 patients and missing data for placebo patients will be imputed under MAR assumption. Missing data after discontinuation of study drug for QAW039 patients will be imputed differently by distinguishing the following two cases:

1. A continued treatment effect for QAW039 150 mg in patients lost to follow-up for reasons likely to be unrelated to study drug (e.g., pregnancy, study terminated by sponsor, technical problems, lost to follow-up) will be assumed (missing at random approach).
2. Same treatment effect as placebo will be imputed for QAW039 150 mg in patients that discontinue study drug and are lost to follow-up due to (or following a study drug discontinuation due to) adverse event, death, physician decision and subject/guardian decision (jump to reference approach).

### **Imputation based on retrieved drop-out data**

Retrieved drop-out data will be used to impute missing post-study drug discontinuation data as a supportive analysis. While retrieved drop-outs may be a particularly suitable basis for imputing data for non-retrieved drop-outs as it is most close to the ITT principal, this analysis may not be feasible or may require simplification of the imputation model, because observed post-study drug discontinuation data may be sparse.

## **5.2 Secondary efficacy variables**

The analyses on the secondary variables may be repeated on the PPS. Subgroup analysis on the secondary efficacy variables for subgroups specified in Section 5.1.1 will be performed outside of CSR.

# **6 Appendix**

This appendix gives details about statistical methods in addition to the report text. All analyses will be performed by using SAS Version 9.4.

*Note: The SAS version that will be actual on the NOVARTIS platform at the time when the study is completed will be stated here.*

## **6.1 Imputation rules**

### **6.1.1 Study drug**

Missing/partial start date or end date of study treatment will not be imputed.

### **6.1.2 AE date imputation**

Rules for imputing AE end date or start date will be provided in Programming Dataset Specification (PDS) document in details.

### **6.1.3 Concomitant medication date imputation**

Rules for imputing concomitant medication start or end dates will be provided in Programming Dataset Specification (PDS) document in details.

### **6.1.3.1 Prior therapies date imputation**

Rules for imputing the prior therapies end date or start date will be provided in Programming Dataset Specification (PDS) document in details.

### **6.1.3.2 Post therapies date imputation**

Rules for imputing the post therapies end date or start date will be provided in Programming Dataset Specification (PDS) document in details.

## **6.2 AEs and Concomitant medications coding/grading**

The MedDRA version which will be available at the time of database lock, will be used for the coding purpose of the adverse events. For coding purpose of the concomitant medications, the available WHO-DD (World Health Organization- Drug Dictionary) version at the time of database lock will be used.

## **6.3 Visit remapping and assessment windows**

If a scheduled visit did not occur, the data from the treatment discontinuation or study discontinuation visit may be used as the data from the scheduled visit, if the treatment discontinuation or study discontinuation visit occurred closer to the planned study day of the missing scheduled visit than to the planned study day of any other scheduled visit. In this case, the treatment discontinuation or study discontinuation visit will be treated as the scheduled visit for the purpose of all analyses so that no missing data imputation will be necessary. Otherwise, the data from any scheduled visit that did not occur will be dealt with like any other missing data. If the treatment discontinuation or study discontinuation visit is not re-mapped to any scheduled visit, it will be treated as an unscheduled visit that does not appear in by-visit summaries.

## **6.4 Laboratory parameters derivations**

The following table shows the criteria for clinically notable laboratory values. Not all parameters have notable criteria defined.

**Table 6-4-1 Direction of interest for worst case value for laboratory parameters**

Laboratory Parameter	Direction of interest for worst case value
A. Hematology	
Basophils	High
Eosinophils	High
Hematocrit	Low
Hemoglobin	Low
Lymphocytes	Low and high
Monocytes	High
Neutrophils	Low and high
Platelets	Low and high
RBC	Low
WBC total	Low and high
B. Chemistry	
Albumin	Low
Sodium	Low and High
Alkaline Phosphatase	High
ALT/SGPT	High
AST/SGOT	High
Bilirubin Total	High
Blood Urea Nitrogen (BUN)	High
CPK	High
Creatinine	High
Gamma GT	High
Glucose	Low and high
Potassium	Low and high
Uric acid	High

**Table 6-4-2 Clinical notable criteria for selected laboratory tests**

Laboratory parameter (unit)	Bound for notably low values	Bound for notably high values
Hematology		
Hematocrit (v/v)		
Male aged 12-17	0.34	
Male aged 18-65	0.37	
Male aged >=66	0.34	
Female aged 12-65	0.32	
Female aged >=66	0.31	

Laboratory parameter (unit)	Bound for notably low values	Bound for notably high values
Hemoglobin (g/L)		
Male aged 12-17	100	
Male aged >=18	110	
Female	95	
Thrombocytes (x10E  /L)	75	700
WBC's (x10  /L)	2.8	16.0
Chemistry		
Alkaline Phosphatase (IU/L)	-	3xULN
Total Bilirubin (µmol/L)	-	34.2
Creatinine (µmol/L)		176.8
Potassium (mmol/L)	3	6
Glucose (mmol/L)	2.78	9.99
ALT/SGPT (U/L)	-	3 x ULN
AST/SGOT (U/L)	-	3 x ULN
BUN/ Urea (mmol/L)		9.99
Sodium (mmol/L)	125	160
Gamma GT (U/L)		3 x ULN
CPK (IU/L)		4 x ULN
Urinalysis		
Dipstick blood		≥ 2+
Dipstick glucose		≥ 2+
Dipstick leukocytes		≥ 2+
Dipstick protein		≥ 2+

v = volume, ULN = upper limit of normal

**Table 6-4-3 Notable liver function test values**

Criterion
ALT > 3 x ULN ALT > 5 x ULN ALT > 8 x ULN ALT > 10 x ULN ALT > 20 x ULN
ALT or AST > 3 x ULN ALT or AST > 5 x ULN ALT or AST > 8 x ULN ALT or AST > 10 x ULN ALT or AST > 20 x ULN
Total Bilirubin > 1 x ULN Total Bilirubin > 1.5 x ULN Total Bilirubin > 2 x ULN Total Bilirubin > 3 x ULN
ALP > 1.5 x ULN ALP > 2 x ULN ALP > 3 x ULN ALP > 5 x ULN
ALT or AST > 3 x ULN and Total Bilirubin > 1.5 x ULN ALT or AST > 3 x ULN and Total Bilirubin > 2 x ULN ALT or AST > 5 x ULN and Total Bilirubin > 2 x ULN ALT or AST > 8 x ULN and Total Bilirubin > 2 x ULN ALT or AST > 10 x ULN and Total Bilirubin > 2 x ULN ALT or AST > 20 x ULN and Total Bilirubin > 2 x ULN
ALP > 3 x ULN and Total Bilirubin > 2 x ULN ALP > 5 x ULN and Total Bilirubin > 2 x ULN
ALT or AST > 3 x ULN and Total Bilirubin > 2 x ULN and ALP ≤ 2 x ULN (Hy's law)
ALT or AST > 3 x ULN and (nausea or vomiting or fatigue or general malaise or abdominal pain or (rash and eosinophilia))*

ALT=alanine aminotransferase; AST=aspartate aminotransferase; ALP=alkaline phosphatase; ULN=upper limit of normal. \*Based on the signs/symptoms information as recorded on the liver events eCRF, not the adverse events eCRF.

## 6.5 Vital signs – definition of clinically notable and relevant values

The following table shows the clinical notable criteria for vital signs.

**Table 6-5-1 Vital signs - clinical notable values**

Vital sign parameter (unit)	Lower bound of clinically notable range	Upper bound of clinically notable range
Notable value considering newly occurring or worsening cases		
Systolic blood pressure (mmHg)	< 75	> 200
Diastolic blood pressure (mmHg)	< 40	> 115
Pulse rate (bpm)	< 40	> 130
Notable change from baseline		
Systolic blood pressure (mmHg)	≤ 90 and decrease from baseline by ≥ 20	≥ 180 and increase from baseline by ≥ 20
Diastolic blood pressure (mmHg)	≤ 50 and decrease from baseline by ≥ 15	≥ 105 and increase from baseline by ≥ 15
Pulse rate (bpm)	≤ 50 and decrease from baseline by ≥ 15	≥ 120 and increase from baseline by ≥ 15
Weight (kg)	Decrease ≥ 7% from baseline	Increase ≥ 7% from baseline

## 6.6 Statistical methodology and assumptions

SAS codes for all statistical methodology described in this section will be included in Table, Figure, Listing (TFL) Shells as programming note.

### 6.6.1 Multiple imputations for primary and secondary variables

The imputation and analysis of primary and secondary variables will be implemented using the “five macros” available from [www.missingdata.org.uk](http://www.missingdata.org.uk) (for a full description see Carpenter et al (2013)). The purpose and activities of each of the five macros is described below.

Part1A declares the parameter estimation model and checks consistency with the input dataset. It builds a master dataset which holds details of the current job and also builds indexes for the classification variables, which may be either numeric or character.

Part1B fits the parameter estimation model using the MCMC procedure and draws a pseudo-independent sample from the joint posterior distribution for the linear predictor parameters and the covariance parameters.

Part2A calculates the predicted mean under MAR, and under MNAR for each subject based on their withdrawal pattern once for each draw of the linear predictor parameter estimates. The choice of MNAR is controlled by the method used, which may vary from subject to subject.

Part2B imputes the intermediate missing values using MAR and the trailing missing values using MNAR, by deriving the conditional distribution for the missing values conditional on the observed values and covariates, using the appropriate sampled covariance parameter estimates.

Part3 carries out a univariate ANOVA analysis at selected time points usually based on the same covariates as the parameter estimation model. It then combines the least-squares means and their differences using the MIANALYZE procedure to provide final results.

This is example code to implement the primary analysis:

```
%part1A(Jobname=fev1
,Data=RE
,Subject=subjid
,Response=aval
,Time=visit
,Treat=trt01pn
,Covbytime= basefev basescore basesaba
,Catcov=stratum
,
);
```

Where subjid = subject identifier

aval = change from baseline in FEV1 value at visit during the treatment epoch

visit = treatment period visit number

trt01pn = planned treatment

basefev = baseline FEV1 value

basescore = baseline daytime asthma symptom score

basesaba = baseline total daily SABA use

stratum = randomization strata (patient age (<18 years or  $\geq$ 18 years), use or not use a second asthma controller at study entry, region)

```
%part1B(Jobname=fev1
,Ndraws=1000
,thin=750
,seed=12345
);
%part2A(Jobname=fev1_J2R
,inname=fev1
,methodV=Mymethod
,refV=Myreference
);
```

where Mymethod = Method used to impute missing data: J2R for QAW patients who discontinued treatment and MAR otherwise. Myreference = Placebo

```
%part2B(Jobname=fev1_J2R
,seed=832216);
```

```
%part3(Jobname=fev1_J2R
,ANTreat=trt01pn
,label=Mixed MAR and J2R);
```

Results will be presented as Least Squares Means (LSM) and standard errors (SE) for treatment effects and LSM, SE, associated two-sided 95% confidence interval, and two-sided p-value for all relevant treatment contrasts.

## 6.7 Rule of exclusion criteria of analysis sets

Subject classification in the analysis sets (FAS, Safety, Per Protocol, SCR, and RAN) will be based on protocol deviation specifications and non-protocol deviation classification criteria as following.

**Table 6-7-1 Protocol deviations that cause subjects to be excluded**

Deviation ID	Description of Deviation	Exclusion in Analyses
INCL01a	Informed consent was not obtained	SCR, RAN, FAS, PPS, SAF
INCL02	Age < 12 years	PPS
INCL03	No current diagnosis of Asthma of at least 6 months prior to V1	PPS
INCL05a	For patients aged >= 18 years, % predicted FEV1 was not <= 85% at both V1 & V101	PPS
INCL05b	For patients aged 12 years to <18 years, % predicted FEV1 was not <= 90% at V1 & V101	PPS
INCL05c	Spirometry done for assessing study eligibility is not meeting ATS/ERS criteria for acceptability or repeatability.	PPS
INCL08	Reversibility not demonstrated before randomization	PPS
EXCL01	Other investigational drug used within 30 days or within 5 half-lives prior to Screening	PPS
EXCL10b	Smoking history of greater than 10 pack years	PPS
EXCL11	Patient had an asthma exacerbation requiring systemic corticosteroids, hospitalization, or emergency room visit within 6 weeks prior to Visit 1	PPS

Deviation ID	Description of Deviation	Exclusion in Analyses
EXCL12	Patient had an asthma exacerbation requiring systemic corticosteroids, hospitalization or emergency room visit during the screening or placebo run-in periods.	PPS
EXCL13	Patients had respiratory tract Infection or asthma worsening within 4 weeks prior to V1.	PPS
COMD01	Prohibited asthma related ConMed during treatment epoch	PPS
COMD04	Permitted asthma related medication not taken as allowed under certain conditions during treatment epoch	PPS
COMD05	Baseline asthma medication or their dose was changed after Visit 1	PPS
OTH04	Patient randomized in error	PPS

**Table 6-7-2 Subject Classification**

Analysis Set	PD ID that cause subjects to be excluded	Non-PD criteria that cause subjects to be excluded
SCR	INCL01a,	NA
RAN	INCL01a	NA
FAS	INCL01a	Not in RAN; Randomized and no double-blind study drug taken
PPS	INCL01a,INCL02,INCL03, INCL05a,INCL05b,INCL05c, INCL08,EXCL01,EXCL10b, EXCL11,EXCL12, EXCL13,COMD01,COMD04 ,COMD05,OTH04	Not in FAS;
SAF	INCL01a	No double-blind study drug taken

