5.6 Study completion and discontinuation

5.6.1 Study completion and post-study treatment

Study completion for a patient will occur after he/she has completed 12 weeks of treatment (through to Visit 299) or has prematurely withdrawn. Completion of the study will be when

all randomized patients have completed 12 weeks of treatment and the post-treatment Follow-up visit.

Patients who have been screened when enrolment target has been met will be allowed to proceed onto study participation.

A Safety Study of QAW039 is planned. At sites participating in the Safety Study, patients who successfully complete 12 weeks of treatment in this study (Study A2317) may be offered participation in the Safety Study; patient participation in the Safety Study will be optional. Patients not entering the Safety study will complete the follow-up period and will not be given further access to study drug because the risk/benefit ratio will not yet have been substantiated and there are already other marketed therapeutic alternatives available to treat these patients. At the time of study completion or early termination, all patients will be placed on the appropriate asthma treatment as prescribed by the investigator.

The investigator must provide appropriate advice on the continued use of effective contraception for at least one week (at least 5 half-lives of QAW039) after the study completion visit (Visit 299) or premature study drug discontinuation and must follow up with the subject as appropriate at least to the end of this period.

The investigator must provide follow-up medical care for all patients who are prematurely withdrawn from the study, or must refer them for appropriate ongoing care.

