5.6.2 Discontinuation of study treatment

Discontinuation of study drug for a patient occurs when study drug is stopped earlier than the protocol planned duration, and can be initiated by either the patient or the investigator.

Patients may voluntarily discontinue study drug (discontinue double-blind study drug but continue with study participation) at any time. **Patients who wish to discontinue double-blind study drug will be asked to remain in the study and complete all study visits. Patients withdrawn from study drug will receive SoC asthma therapy according to investigator judgment.**

The investigator must discontinue study drug for a given patient if, on balance, he/she believes that continuation of study drug would negatively impact the risk/benefit of trial participation.

Study drug **must** be discontinued under the following circumstances:

- Patient wish;
- Pregnancy (see [Section 6.5.6](#) and [Section 7.6](#));
- Any situation in which study participation might result in a safety risk to the patient;
- Female patients non-compliant with the chosen effective method of contraception during the study. The investigator must provide appropriate advice on the continued use of effective contraception for at least one week (at least 5 half-lives of QAW039) after study drug discontinuation and follow up with the subject as appropriate at least to the end of this period;
- Liver laboratory test abnormality / event (see [Appendix 2](#));
- Abnormal liver laboratory results requiring discontinuation – refer to [Table 14-2](#);

- If the investigator considers it appropriate after the confirmation of a liver safety monitoring signal:
 - ALT or AST ≥ 5 xULN, **or**
 - ALT or AST ≥ 2.5 xULN **and** total bilirubin ≥ 1.5 xULN ([Appendix 2](#));
- Any laboratory abnormalities that in the judgment of the investigator, taking into consideration the subject's overall status, prevents the subject from continuing participation in the study;
- Premature unblinding of study drug for a patient for any reason;
- Total white blood cell count <1000 cells/ μ L;
- If patients on statin therapy complain of persistent muscle pain without any obvious cause for greater than 3 days accompanied by increase in CK levels >10 x ULN or persistent intolerable muscle pain regardless of the accompanying CK level;

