9.1 Analysis sets

The screened set (SCR) will include all patients who provided informed consent.

The full analysis set (FAS) will include all randomized patients who received at least one dose of study drug. It was considered reasonable to limit the FAS to patients who took trial medication, because the decision on whether or not study drug is started will not be influenced by the treatment group assignment due to the effective treatment blinding procedures described in [Section 5.4](#). Following the intent-to-treat principle, patients will be analyzed according to the treatment they were assigned to at randomization.

The per-protocol set (PPS) will include all patients in the FAS without any major protocol deviations such as violation of major entry criteria or low compliance. Patients may also be considered censored for the PPS analysis at the time of major post-baseline protocol deviations. Major protocol deviations will be defined in the study specification document

prior to database lock and the un-blinding of the study. Patients will be analyzed according to the treatment they received.

The safety set (SAF) will include all patients who received at least one dose of double-blind study drug. Patients will be analyzed according to the treatment they received.

The analysis of the primary objective will be performed on the FAS. The PPS will be used for the supportive analysis of the primary and the secondary variables. The FAS will be used for the analysis of all other efficacy variables. The SAF will be used in the analysis of all safety variables.

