## 2.2 Analysis sets

The following analysis sets are defined:

- The screened set (SCR) will include all patients who provided informed consent.
- The randomized (RAN) set will consist of all patients who were assigned a randomization number, regardless of whether or not they actually received study medication. Patients in RAN will be analyzed according to the treatment they were randomized to.
- The Full Analysis Set (FAS) will consist of all randomized patients who received at least one dose of study medication. It was considered reasonable to limit the FAS to patients who took trial medication, because the decision on whether or not study drug is started will not be influenced by the treatment group assignment due to the effective treatment blinding procedures. Following the intent-to-treat principle, patients will be analyzed according to the treatment they were assigned to at randomization. The FAS will be used for the analysis of all efficacy endpoints, and for the summaries of patient disposition, demographic and baseline characteristics.
- The Per-Protocol Set (PPS) will include all patients in the FAS who did not have any major protocol deviations such as violation of major entry criteria. Protocol deviations will be defined in the data review plan document prior to database lock and the un-blinding of the study. Protocol deviations leading to exclusion from analysis sets are

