#### **2.4.1.2 Compliance**

Study drug compliance will be assessed. The overall compliance will be calculated as the percentage of days with study medication intake during the period from first intake to last intake taking into account the duration of the drug interruptions.

Percentage of days with study medication intake =  $100 \times \text{number of days with study medication intake as per protocol} / (\text{Date of last known dose of study drug} - \text{Day 1} + 1)$ .

Compliance will be categorized as <80%, 80% -100% and summarized by treatment group for the safety set.

Time to study treatment discontinuation will be displayed graphically for each treatment group using a Kaplan-Meier curve for the SAF. The date of study treatment discontinuation is defined as the date of last dose of study medication. Patients who completed the study treatment will be censored at the final visit for treatment period.

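### The SAP's per-protocol set has no exclusion for low study-drug compliance, which the protocol names, and its background-medication rule COMD05 has no end point

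*SAP*

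**What the plan says.** Protocol 9.1 defines the PPS as FAS patients "without any major protocol deviations such as violation of major entry criteria or low compliance". It adds an alternative to outright exclusion: "Patients may also be considered censored for the PPS analysis at the time of major post-baseline protocol deviations". The detailed list is left to a later document, to be settled before database lock and unblinding.

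SAP 2.2 defines the PPS as FAS patients who "did not have any major protocol deviations such as violation of major entry criteria"; low compliance is no longer an example. Membership is set out in SAP 6.7. The PPS row of Table 6-7-2 ends with "EXCL11,EXCL12, EXCL13,COMD01,COMD04 ,COMD05,OTH04", and its only criterion that is not a deviation is absence from the FAS. SAP 2.4.1.2 derives a compliance percentage ("Compliance will be categorized as <80%, 80% -100"%), but only to summarise it by arm in the safety set.

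In Table 6-7-1, COMD05 reads "Baseline asthma medication or their dose was changed after Visit 1". Its neighbours COMD01 and COMD04 are confined to the treatment epoch.

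On background therapy, Protocol 3.1 and 5.1.2 allow no change during the study. Protocol 5.6.2 says "Patients withdrawn from study drug will receive SoC asthma therapy according to investigator judgment". Protocol 5.6.1 says that at study completion or early termination "all patients will be placed on the appropriate asthma treatment as prescribed by the investigator".

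**The concern.** A per-protocol analysis is there to show the effect in patients who took the drug and followed the plan. If patients who missed many tablets stay in, they are in both the FAS and the PPS, and comparing the two says nothing about poor intake. The protocol already treats 80% as the standard: under exclusion criterion 30 a patient below 80% in the run-in cannot be randomised, yet one below 80% for the whole treatment period is kept in the PPS.

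COMD05 has the opposite fault. A rule with a start and no end can exclude a patient for something that happens after the endpoint has been measured. Exclusions of that kind cost patients without making the set any more per protocol.

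**Working it through.** No figure in the plan is disputed. The check compares the texts, then gives a sense of scale.

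**Compliance exclusion**
- Protocol 9.1: low compliance is named.
- SAP 2.2: the corresponding sentence omits it.
- Tables 6-7-1 and 6-7-2: the PPS codes are INCL01a, 02, 03, 05a, 05b, 05c, 08; EXCL01, 10b, 11, 12, 13; COMD01, 04, 05; and OTH04. That is 7 + 5 + 3 + 1 = 16. COMD04 concerns permitted asthma medication, not study drug.
- SAP Section 4 lists changes as small as how age is obtained, but not this one.

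The SAP formula is 100 × days with intake / (last dose date − Day 1 + 1). Two illustrative patients:
- Takes half the doses through Day 84: 100 × 42/84 = 50%. In the PPS as written; an 80% code would remove this patient.
- Takes every dose for 28 days, then stops: 100 × 28/28 = 100%. In the PPS as written, and an 80% code would not remove this patient. The derivation stops at the last dose, so early stoppers need a separate rule.

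**COMD05 window**
- COMD01 and COMD04: treatment epoch. COMD05: from Visit 1, no end.
- Protocol 5.6.1 places a patient's study completion at Visit 299 (Week 12), and Protocol 3.1 has a 4-week follow-up after the last dose for patients not entering the safety study. A background change in that interval meets the wording of COMD05, although the Week 12 FEV1 is already recorded.

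**Scale**

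The plan's 15% discontinuation rate can be checked against its stated power of 90.3%. With 325 per arm, SD 380 mL, two-sided 5%, and no effect in the 15% who stop, the effect is 112 × 0.85 = 95.2 mL and the two-sample power is 89.1%. That is close enough to take the plan's inputs as given.
- Stopping study drug: 650 × 0.15 = 97.5. Half with a Week 12 FEV1: 97.5 × 0.5 = 48.75, about 49. COMD05 could reach these retrieved drop-outs before Week 12, but only those whose background therapy is changed.
- Low compliance: the documents give no rate. Assume 5% to 15% of patients average 50% intake and that the effect is proportional to intake. A 112 mL effect in adherent patients then appears as 112 × (1 − 0.05 × 0.5) = 109.2 mL down to 112 × (1 − 0.15 × 0.5) = 103.6 mL, a loss of 2.8 to 8.4 mL. If instead 5% to 20% were non-adherent with no effect at all, it appears as 112 × 0.95 = 106.4 mL down to 112 × 0.80 = 89.6 mL.
- For comparison, the standard error of the difference is about 380 × √(2/325) = 29.8 mL, before covariate adjustment.

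**The case against.** The best defence is that nothing confirmatory depends on the PPS. The primary analysis is on the FAS. Where Protocol 9.4.4 says the PPS analyses will be done, SAP 2.5.5 says the primary one may be, and SAP 5.2 makes the secondary ones optional and places them outside the CSR. This stands, and it limits the weight of the point.

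Second, low compliance is only an example in Protocol 9.1, which leaves the list to a later document; SAP 2.2 likewise refers to a data review plan. The copy of SAP 2.2 available here also breaks off just after the PPS definition. That leaves the sponsor free to define low compliance. It does not explain why a named example has no counterpart in Tables 6-7-1 and 6-7-2, which are complete, and no entry in Section 4.

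Third, compliance is summarised by arm, and SAP 2.5.5 has an on-treatment MMRM. The MMRM deals with patients who stop. It keeps those who miss doses without stopping.

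Fourth, a reader might infer that COMD05 removes patients who were managed as the protocol directs. The documents do not go that far. Protocol 5.6.2 permits a change of background therapy after study drug is stopped but does not require one. Table 6-7-1 lists protocol deviations, and a change that 5.6.1 or 5.6.2 provides for may never be logged as one. Table 6-1 also schedules no concomitant-medication review at Visit 301, although Protocol 5.5.7 still requires recording. What remains is that COMD05 states no such exception and no end.

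Fifth, ending COMD05 at the last dose of study drug would be a poor repair. It would bring patients who are off drug and on altered background therapy back into the PPS, which is the dilution the compliance exclusion is meant to prevent. This is right, and the fix below avoids it.

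**Conclusion.** Two drafting faults hold. The SAP's PPS departs from Protocol 9.1 by having no study-drug compliance exclusion, and the departure is unrecorded. COMD05 has no end point, so on its wording it can exclude patients for changes after the Week 12 assessment.

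The consequences are confined to a supportive, optional analysis. It would be wrong to infer that the primary result, the alpha allocation or the success criterion is affected. Nor is 49 a forecast of exclusions: it is a ceiling on retrieved drop-outs reached before Week 12, resting on the plan's 15% and one-half, and the documents give no rate of background change among them or among completers after Visit 299. The dilution figures rest on assumed rates and an assumed link between intake and effect. Over 5% to 15% at half intake, the loss is well below one standard error.

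The faults merit correction because the remedy is cheap and PPS membership settled after unblinding would carry little weight.

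**What to change.** Before unblinding:
1. Add a PPS-exclusion code to Tables 6-7-1 and 6-7-2 for overall study-drug compliance below 80% as derived in SAP 2.4.1.2, and restore low compliance to the definition in SAP 2.2.
2. Because that derivation runs only to the last dose, adopt the censoring option of Protocol 9.1: censor PPS data at study-drug discontinuation or another major post-baseline deviation. State how censored values are then treated, since the primary imputation in SAP 2.5.4 would fill them on the placebo profile for QAW039 patients.
3. End the COMD05 window at the Week 12 (Visit 299) assessment, and handle changes after study-drug discontinuation by the same censoring.
4. Reconcile Protocol 3.1 and 5.1.2 with 5.6.1 and 5.6.2 on background therapy after study drug is stopped, so that it is clear which changes are deviations. Which rule should apply is for the sponsor to settle.

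The cost is SAP wording, one flag from an existing derivation, a censoring rule for the PPS and a protocol clarification. No new data are needed. The PPS may become somewhat smaller or larger.
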